## 9.2 Toxicity associated with Enadenotucirev

Below is a summary table of commonly reported treatment related adverse events (≥10% patients) by incidence and preferred term following IV infusion of enadenotucirev at the doses used in the trial. Further explanation can be found below the table.

Preferred Term	Dose level (1 x10  )	Dose level (3 x10  )
Pyrexia	39%	75%
Chills	33%	75%
Fatigue	6%	35%
Nausea	17%	40%
Asthenia	39%	25%
Vomiting	17%	30%
Decreased Appetite	17%	45%
Diarrhoea	11%	10%
Flu like illness	6%	30%
ALT increased	0 %	5%
Fibrin d-dimer increased	0%	20%

Hypertension	0 %	30%
Musculoskeletal pain	11%	10%
AST increased	0%	5%
Thrombocytopenia	6%	5%
Neutropenia	22%	0%
Platelet count decreased	6%	10%
Proteinuria	0%	20%
Headache	11%	10%

### Inflammatory/influenza-like Symptoms

Pyrexia has been reported in the majority of patients at doses of  $1 \times 10^{12}$  vp. Chills are very common above  $1 \times 10^{12}$  vp. Additionally, influenza-like illness, the diagnostic term used when multiple symptoms including pyrexia and chills were reported, has been reported frequently at these doses. These symptoms usually have onset shortly after dosing and are manageable with antipyretic medication. Other symptoms typical of an influenza-like illness such as myalgia, arthralgia and musculoskeletal pain have been reported across the dose range but much less frequently. These events have not been reported as SAEs. General symptoms such as asthenia, fatigue and malaise may be attributed to an inflammatory response to viral particles but are also frequently seen in cancer patients. They were commonly reported in the studies with enadenotucirev but with no clear dose relationship. Gastrointestinal symptoms such as nausea, vomiting and diarrhoea may also be attributed to an inflammatory response to viral particles. The incidence of diarrhoea was predominantly above the MTD. Nausea and vomiting appeared dose-related with an increase in frequency at doses of  $3 \times 10^{12}$  vp and above. There was one non-serious CTCAE Grade 2 infusion-related reaction after the first dose of  $6 \times 10^{12}$  vp. The details are unknown but no action was required and the patient continued to receive enadenotucirev.

### 9.3 Management of enadenotucirev toxicity

Nausea and vomiting should be treated with antiemetics and hydration as per institutional protocol.

Flu-like syndrome should be treated with supportive measures, antipyrexials (e.g. paracetamol) and hydration. If acute respiratory symptoms such as hypoxia develop then symptomatic treatment with supplemental oxygen and bronchodilators may be used if clinically indicated. Hospitalisation for observation during the dosing period may be considered according to Investigator judgement and circumstances of the patient.

Antivirals may be used to treat patients that exhibit prolonged and/or difficult to manage toxicity that is thought to be due to viral replication. High dose steroid therapy may be required to manage the associated inflammatory response.

**Diarrhoea:** It is strongly recommended that all patients have loperamide prescribed prior to commencement of treatment, in case of development of diarrhoea. Loperamide is recommended as the initial antidiarrhoeal medication. Patients should be instructed to contact the trial site for further guidance if diarrhoea is not controlled after 12 hours of loperamide treatment. Codeine phosphate up to 30 mg 4 times a day can be added if diarrhoea is not controlled with 16mg of loperamide per day.

**Serious infusion reaction:** These have been observed in a small number of participants in previous trials of enadenotucirev, appearing to reflect cytokine responses to treatment. Infusion reactions are more common with the first infusion, although reactions cannot be excluded on subsequent infusions, even if no reaction was seen during the first. In the event of a serious infusion reaction discontinue the infusion and monitor and treat the patient as per standard local protocol for management of cytokine release syndrome (e.g. vigilant supportive care, maintenance of adequate hydration and blood pressure, and corticosteroids and or other appropriate immunosuppression). Extensive comorbidities and older age should be closely monitored for cardiac function and immunosuppression should be instituted earlier. Cytokine release syndromes of grade 3 or higher are considered a DLT so no further drug should be administered.

**Renal injury:** Three patients out of 123 patients (2.4%) have developed significant renal impairment while receiving enadenotucirev. Whilst no confirmed pathophysiology has been identified it is felt to be due to vascular leakage due to cytokine release. Proteinuria of 2+ on a urine dipstick should therefore be further investigated, due to the potential risk of serious renal injury, with 24 hour urine collection for protein/creatinine ratio. If preferable locally, a urine protein- to-creatinine ratio or urine albumin – to – creatinine ratio are also acceptable in lieu of a 24 hour collection test. Additional blood tests should also be up to date including a serum albumin and serum creatinine. A consultation with nephrology is advised for specialist input. Specifically, early specialist intervention for investigation and treatment if decline in renal function is detected will include:

1. Full renal work-up, including examination of urine sediment, discussion with renal team and then commence high dose corticosteroids and then, if further decline in renal function;
2. Renal biopsy, followed by plasmapheresis should be considered with close involvement of the renal team.

No enadenotucirev is to be administered after the development of proteinuria as this constitutes a DLT.

Refer to section 8.5 for guidance on dose modification/ interruption due to toxicity.

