#### **Renal:**

- Development of proteinuria, 2+ as measured by urinalysis and confirmed with an albumin/creatinine ratio of  $>3\text{g}/\text{mmol}$  with a 24-hour urinary protein  $\geq 1\text{g}/24\text{h}$  or if there is a decline in eGFR (where a decline in eGFR is defined as eGFR  $<60\text{ml}/\text{min}/1.73\text{m}^2$  or a drop in eGFR by 20% from screening, baseline or previous visit), following administration of enadenotucirev, shall be classified as a DLT. No further doses of enadenotucirev will be administered to that patient.

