# 6. ANALYSIS

## 6.1 Outcome Definitions

Primary outcome:

- *Safety*: Binary toxicity measure defined by the occurrence of a DLT or not. This is recorded during the 13 weeks of follow-up after starting treatment. The definition of a DLT is given Appendix 4.
- *Efficacy*: MRI tumour regression grade. This is a 5 point scale that is coded as a binary variable, with scores of 1 or 2 defining a responder and scores of 3, 4 or 5 a non-responder. It is measured at 13 weeks. Patients who did not have the evaluation, or who withdrew or died prior to evaluation will be treated as non-responders. During the trial, for dose-escalation decisions a patient who has not yet reached this time point will not be included in analysis at this decision point. See Appendix 5 for the definition of MRI tumour regression grade

See Section 6.2.1 Primary analysis for definition of the optimal dose.

For dose-escalation interim analyses the safety and efficacy data is taken from the patient status update CRF. For the final determination of the MTD at the end of the trial, the safety outcome will be taken from the *BW135\_DLT\_Assessment* and *BW166\_Adverse\_Events* CRFs and the efficacy outcome taken from the *BW156\_Week13\_Pelvic\_MRI* CRF.

Secondary outcomes:

- Treatment tolerance. This is the amount of capecitabine and radiotherapy received, coded as completing at least 80% of the intended capecitabine dose and at least 20 fractions of radiotherapy. Measured at week 9. Compliance is taken from the *BW150\_Capecitabine* and *BW145\_Radiotherapy* CRF.
- MRI tumour regression grade. See definition for primary outcome, but here it will not be dichotomised. MRI tumour regression grade is taken from the *BW156\_Week13\_Pelvic\_MRI* CRF.
- Pathological complete response. This variable relates to the resected tumour so will only be observed for patients undergoing surgery. It is measured on a 4 point scale, with a score of 1 denoting pathological complete response, and scores 2:4 denoting no pathological complete response. Pathological complete response is taken from the *BW156\_Week13\_Pelvic\_MRI* CRF.
- Neoadjuvant Rectal (NAR) score. This score ranges from 0-100 with a higher score equating to a worse prognosis. It is a derived outcome which components measured on the resected tumour and at initial tumour staging. Therefore, this will only be observed for patients undergoing surgery. It is defined as

- $NAR = \frac{[5pN - 3(cT - pT) + 12]^2}{9.61}$ , where

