### 13. APPENDIX 4 DEFINITION OF DLT

Definition of DLT as given in Protocol V3.0, 11th August 2019

All patients who have received at least one dose of enadenotucirev will be evaluable for DLTs.

DLTs are defined as any of the following occurring between the start of trial treatment until the Week 13 visit and by the principal investigator (PI) assessed as possibly, probably or definitely related to enadenotucirev or the interaction between enadenotucirev and radiotherapy and/or capecitabine. Patients who experience a DLT will receive no further trial treatment.

Dose limiting toxicities must be reported within 24 hours of the site becoming aware using the SAE form and scan and email as a PDF attachment to [[contact]](mailto:[contact]) and send an email notification to [[contact]](mailto:[contact]).

DLTs will be defined as per NCI CTCAE v4.03, except for proteinuria, and include:

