**Renal:**

- Development of proteinuria, 2+ as measured by urinalysis and confirmed with an albumin/creatinine ratio of  $>3\text{g}/\text{mmol}$ , following administration of enadenotucirev, shall be classified as a DLT. No further doses of enadenotucirev will be administered to that patient.

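### The renal DLT has a wrong-looking unit in Protocol 9.1 and SAP Appendix 4, an outdated definition in Appendix 4, and a closing sentence in 9.3 with no threshold

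*Protocol*

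**What the plan says.** **Protocol 9.1, Renal.** The event is a 2+ dipstick confirmed by an albumin/creatinine ratio above 3 g/mmol together with 24-hour urinary protein of at least 1 g, "or if there is a decline in eGFR". The decline is defined as eGFR below 60 "or a drop in eGFR by 20% from screening, baseline or previous visit". Section 9.1 takes proteinuria out of CTCAE grading, so this bullet is the specific rule for it.

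**Protocol 9.3, Renal injury.** "Proteinuria of 2+ on a urine dipstick should therefore be further investigated", by 24-hour collection; spot ratios "are also acceptable in lieu of a 24 hour collection test". The renal text then states: "No enadenotucirev is to be administered after the development of proteinuria as this constitutes a DLT". No level of proteinuria is attached.

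**Protocol 5.3.1 and 8.5.** At 2+, dosing is interrupted until a 24-hour collection has ruled out significant proteinuria (5.3.1), or is delayed and/or discontinued (8.5). Both refer to 9.3.

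**Protocol 4.1, inclusion criterion 8.** The same ratio is given as 3 mg/mmol, and it is also paired with a 24-hour limit of 1 g.

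**SAP.** Section 6.1 states: "The definition of a DLT is given Appendix 4". Appendix 4 is headed "Definition of DLT as given in Protocol V3.0". Its renal bullet reads "Development of proteinuria, 2+ as measured by urinalysis and confirmed with an albumin/creatinine ratio of" more than 3 g/mmol, with no 24-hour protein and no eGFR condition.

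**The concern.** DLT status is the binary outcome of the toxicity model. It feeds every dose recommendation, the early stopping rule and the final dose. A definition with an unreachable limit, or one that differs between the protocol and the SAP, means that the same laboratory results can be coded in two ways.

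The 9.3 sentence also bears directly on care. Sites are sent to 9.3 when a 2+ result appears. Read literally, it bars further enadenotucirev for a patient whose work-up turns out negative. Under 5.3.1 and 8.5 the same patient could be dosed again. Section 9.3 itself reports significant renal impairment in 3 of 123 patients (3/123 = 2.4%, which reproduces), so the rule is there for a real hazard.

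**Working it through.** **1. The unit.** Daily albumin = ratio × daily creatinine excretion. The documents give no creatinine figure; 6 to 16 mmol/day is assumed.

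- As printed: 3 g/mmol × 6 = 18 g/day; 3 g/mmol × 16 = 48 g/day.
- As in criterion 8: 0.003 g/mmol × 6 = 0.018 g/day; 0.003 g/mmol × 16 = 0.048 g/day.
- The 24-hour limit of 1 g, expressed as a ratio: 1000/16 = 62.5 to 1000/6 = 167 mg/mmol.

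The two units differ by a factor of 1000. At 3 g/mmol the 24-hour limit of 1 g adds nothing, because any patient over the ratio limit is far above it. At 3 mg/mmol the pairing makes sense: a sensitive first test followed by a stricter second one.

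**2. The definitions side by side.** Patient with a 2+ dipstick, relatedness accepted, ratio read as mg/mmol:

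| Ratio | 24-h protein | eGFR | Protocol 9.1 | SAP App. 4 | 9.3 read literally |
|---|---|---|---|---|---|
| >3 | ≥1 g | either | DLT | DLT | DLT |
| >3 | <1 g | decline | DLT | DLT | DLT |
| >3 | <1 g | stable | **not a DLT** | **DLT** | DLT |
| ≤3 | <1 g | decline | depends on reading | not a DLT | DLT |
| ≤3 | <1 g | stable | not a DLT | not a DLT | DLT |

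A ratio of 3 or less with 24-hour protein of at least 1 g is left out. By step 1 the two nearly contradict each other, non-albumin protein aside.

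The third row is the clear conflict between protocol and SAP. The fourth row shows the ambiguity in 9.1: an eGFR decline may replace only the 24-hour result, or may count without the ratio. Above the ratio limit, both readings of 9.1 give the same answer.

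With the unit as printed, realistic patients all fall below the ratio limit. Appendix 4 then yields practically no renal DLT. Protocol 9.1 yields one only if an eGFR decline counts without the ratio.

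**3. What one recoded DLT can do.** Inputs from SAP 6.2.1: logit(DLT probability) = log α + β log(x/6), schedule codes 1, 2, 4, 6; log α ~ N(log(0.3/0.7), variance 1.44); log β ~ N(−0.1, variance 0.25). The pick is the schedule with the highest posterior probability of a rate in (0.2, 0.35), among those with P(rate > 0.35) < 0.35. The posterior was computed on a grid with all weights 1.

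Illustrative data: 3 DLT-free patients on each of schedules 1 and 2, and 6 patients on schedule 3.

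| DLTs on schedule 3 | P(rate > 0.35) at schedule 4 | Toxicity pick |
|---|---|---|
| 1 | 0.17 | 4 |
| 2 | 0.38 (fails 0.35) | 3 |

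With 2 to 8 patients on schedule 3, a first DLT moves the pick at one of seven sizes (n = 2). A second moves it at five of seven (n = 2 to 6). That is 6 of 14 steps.

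The overall recommendation is the lower of the toxicity and efficacy picks. In the example, responses of 1/3, 1/3 and 2/6 lead the efficacy model to schedule 4, so the recommendation moves. With 1/3, 1/3 and 1/6 it picks schedule 1, and nothing changes.

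**The case against.** **9.3 is shorthand.** Section 9.1 is the titled definition, and 9.3 is a management section that orders a work-up and then refers to 8.5. A reader might infer that 9.3 sets a rival DLT with no threshold. The work-up makes sense only if it can come back negative, so the documents do not support that. The sentence still gives a dosing instruction and a DLT label without pointing to 9.1.

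**Appendix 4 is version lag.** It says that it follows Protocol V3.0, so this is the likely cause. A reader might infer that the statistician will recode events from Appendix 4. SAP 6.1 instead takes DLTs from CRFs, after assessment by the principal investigator or designee and discussion with the Chief Investigator and Trial Management Group. That limits uneven coding. But the documents do not say which text the DLT CRF follows, and Appendix 4 is the definition that the SAP cites.

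**14.4 also disagrees.** It has no renal row among its DLTs, and its row for expected non-dose-limiting events points to 9.2, which lists proteinuria. A reader might count this as another conflict. It is a reporting summary that also omits other 9.1 DLTs (anaemia, ALT/AST above 5 × ULN, cystitis, haematuria), and it has catch-all rows. It is not evidence of a renal error.

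**Miscoding would fall on schedules 3 and 4.** Section 9.2 gives proteinuria in 0% at 1×10^12 and 20% at 3×10^12, which invites this. Those figures are ungraded and given without denominators, and Section 1.2 says that the later renal findings appear unrelated to dose or schedule. The inference is not established.

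**The model result is not specific to renal events.** This stands. Any reclassified DLT has the same effect. The example also needs six fully followed patients on schedule 3 and none on 4, which the escalation rules would not often produce.

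**Conclusion.** The point holds as a drafting error inside a primary endpoint. The printed unit is almost certainly wrong: it is 1000 times the eligibility value, and it makes the paired 24-hour limit pointless. The sponsor should confirm this. Appendix 4 and 9.1 disagree on one realistic type of patient if mg/mmol is meant. The 9.3 sentence, though probably shorthand, conflicts with the hold in 5.3.1 and 8.5 and leaves open whether a patient with a negative work-up may be dosed again. Some held patients would become DLTs anyway, by missing two consecutive doses for enadenotucirev toxicity.

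The effect on the trial is possible but not quantified. One recoded event can shift the toxicity pick by one schedule in some data states, and the overall recommendation only when the efficacy model does not already pick a lower schedule. A reader might infer that dose recommendations are likely to be wrong. The documents do not support that, because they do not show how often a discordant renal case would occur.

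The size of the unit error rests on the assumed 6 to 16 mmol of creatinine a day. The model example rests on illustrative data with full follow-up. The textual conflicts rest on neither.

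**What to change.** 1. Correct the ratio unit to mg/mmol in Protocol 9.1 and SAP Appendix 4, once the sponsor confirms it.
2. Punctuate the 9.1 bullet so that it is clear whether an eGFR decline counts without the ratio.
3. Replace the Appendix 4 DLT text with the current 9.1 text. This also aligns febrile neutropenia, which is above 38.5 °C in the SAP but a single reading above 38.3 °C or a sustained 38 °C or more in 9.1.
4. Change the closing DLT sentence of the 9.3 renal text to refer to proteinuria meeting the renal DLT definition in 9.1.
5. Recheck any 2+ case already coded.

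Optional clarifications: a renal row in 14.4 that points to 9.1, and the spot-ratio value that stands in for 1 g/24 h when no collection is done. The latter needs a clinical threshold, which is the sponsor's to set.

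The cost is one bullet and one sentence in the protocol, one SAP appendix, and a short data check. No sample size or model change is needed. Because the text defines a primary endpoint, the sponsor should judge under Protocol 23.4 whether the amendment is substantial.

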#### **aPTT Prolongation**

If at any time a patient has Grade 2 or 3 aPTT prolongation, planned biopsies and IT treatment should not go ahead until the results of the following tests have been received:

1. aPTT 1:1 mixing studies (required for real-time treatment decisions)
2. Hexagonal phase phospholipid (Staclot Lupus Anticoagulant) assay (or local equivalent test for Lupus Anticoagulant) (required for real-time treatment decisions)

If Lupus Anticoagulant is not shown to be present, planned biopsies and IT treatment may not go ahead. If Lupus Anticoagulant is shown to be present, planned biopsies and IT treatment may go ahead (provided that the other clotting parameters such as platelet count and International Normalised Ratio and/or prothrombin time are within acceptable ranges).

In addition, the following analyses will be conducted:

1. Anti-cardiolipin antibodies by enzyme-linked immunosorbent assay (ELISA) (immunoglobulin G [IgG] and immunoglobulin M [IgM])
2. Anti-beta2-glycoprotein I antibodies by ELISA (IgG and IgM)
3. Additional laboratory testing for further characterisation of Lupus Anticoagulant

Patients with aPTT prolongation should be followed up every 2 months until aPTT has normalised to Grade 1 or less, or disease progression.

Once confirmed, tests for Lupus Anticoagulant do not need to be repeated.

#### **9.4 Toxicity associated with capecitabine**

##### **Haematological toxicity**

Myelosuppression is uncommonly observed with capecitabine. Neutropenia and thrombocytopenia should be monitored according to the recommended protocol and appropriate dose modifications made. Anaemia may occur cumulatively and should be corrected during radiotherapy to maintain the haemoglobin > 10g/dL. The FBC should be taken and reviewed (up to 3 days) prior to Day 1 of each cycle of chemotherapy.

##### **Gastrointestinal toxicity**

Nausea and vomiting is an overlapping toxicity of both capecitabine and enadenotucirev. Anorexia, nausea and occasional vomiting may persist. Nausea occurs less commonly with capecitabine. Diarrhoea occurs with capecitabine and patients should receive advice regarding discontinuation of therapy and use of loperamide or codeine phosphate (see section 9.3). Clinicians should be aware of infective causes of diarrhoea (e.g. Clostridium difficile), and patients should be tested in cases of concern. Antibiotic treatment is not recommended routinely but may be required in such circumstances. Stomatitis occurs with capecitabine and patients should receive advice regarding good oral care, and the use of mouthwash (e.g. Corsodyl™).

##### **DPYD deficiency**

If a patient has not received capecitabine in the past DPD testing should be undertaken as per Institutional protocol. Patients with partial or full DPD deficiency are not eligible for the study. Occasionally (approximately 1-3%) a patient may have a markedly exaggerated toxicity due to reduced 5FU catabolism. If this occurs, await full recovery of toxicities. Further treatment should be discussed with the Chief Investigator or one of the clinical co-investigators.

#### **9.5 Management of capecitabine toxicity**

Toxicity due to capecitabine administration may be managed by symptomatic treatment and/or modification of the dose as per standard of care. Further information on dose modification is provided in section 8.5. Patients taking capecitabine should be informed of the need to interrupt treatment immediately if moderate or worse toxicity occurs. Detailed information can be found in the product SPCs available from [www.medicines.org.uk](http://www.medicines.org.uk)

## 10 OTHER TREATMENTS (NON-IMPS)

### 10.1 Support medication

Local anti-emetic and anti-diarrheal policy may be followed. Medications for the standard management of symptoms or supportive care for cancer or for the management of the effects of enadenotucirev may be administered at the Investigator's discretion; unless they are excluded concomitant medications.

**Antipyretic prophylaxis:** Subjects must receive antipyretic prophylaxis and hydration at the time of each injection of enadenotucirev (as per section 8.3) unless clinically excluded (e.g. allergic to paracetamol, when alternatives should be used such as NSAIDS).

### 10.2 Concomitant medication and non-drug therapies

Concomitant medication may be given as medically indicated. All patients will be asked to provide a complete list of prescription and over-the-counter medications that have been taken within the previous 4 weeks prior to the first treatment visit. They must also inform the Investigator about any new medication started while in the trial.

